11.3. Effectiveness Analysis

The primary effectiveness endpoint will be evaluated using the Win Ratio method of analysis for a

hierarchical composite endpoint based on the Finkelstein-Schoenfeld test (Finkelstein and Schoenfeld, 1999; Pocock, et al., 2012) with three components ranked in order of clinical importance: a) fatal bleeding events occurring within 48hrs post-index procedure, b) moderate, severe, or massive perioperative bleeding events according to the Universal Definition of Perioperative Bleeding in Cardiac Surgery (UDPB) classification ≥ 2 , and c) 24-hour chest tube drainage (mL) following surgery. [14] [15] The Win Ratio assigns “wins”, “losses”, or “ties” in sequential comparisons between treatment and control arm subjects according to the hierarchical order of the components of the primary composite endpoint.

There are two key advantages to the Win Ratio method of analysis. First, the hierarchical assessment of the individual components of the composite endpoint according to their clinical significance. Second, the opportunity for different types of components, such as categorical versus continuous, to all be included thereby capturing all available information from each component to increase statistical power.[15] A Win Ratio along with a two-sided 95% CI will be estimated, and a Win Ratio greater than 1.0 favors the treatment arm; when the lower bound of a two-sided 95% confidence interval (CI) around the ratio exceeds 1.0, the treatment is shown to be statistically superior to control at alpha = 0.05.[16] The primary effectiveness analysis will use a combined DOAC population to evaluate the difference between the SOC (control) arm and the DrugSorb-ATR (investigational) arm. The key secondary effectiveness endpoints are drug removal endpoints, namely the percent change in pre-CPB vs. post-CPB apixaban and rivaroxaban levels as measured by liquid chromatography/tandem mass spectrometry (LC/MS-MS). Blood samples for drug removal analyses will be collected and analyzed by a central core laboratory.

Change from baseline in blood concentration of apixaban or rivaroxaban is defined as:

$$\frac{\text{pre-CPB [apixaban]blood} - \text{post-CPB [apixaban]blood}}{\text{pre-CPB [apixaban]blood}} * 100\%$$

and

$$\frac{\text{pre-CPB [rivaroxaban]blood} - \text{post-CPB [rivaroxaban]blood}}{\text{pre-CPB [rivaroxaban]blood}} * 100\%$$

Benchtop studies of drug removal by DrugSorb-ATR (data on file, CytoSorbents Corporation) demonstrate concentration and time dependent absolute drug removal, which are nearly identical for both apixaban and rivaroxaban. Based on these benchtop studies, a conservative estimate of 40% reduction in blood concentration of DOAC between pre- and post- DrugSorb-ATR removal is expected, with a standard deviation of 40%, in the treatment arm. Minimal change is expected in the control arm. A two-sample t-test will be used to evaluate the difference between treatment arms. Due to highly variable baseline drug levels in the study population, percent change from baseline will be analyzed as opposed to observed values.

Additional secondary endpoints include 24-hour CTD (volume [mL]), total platelet transfusions during the index hospitalization (volume [mL] and units), and total PRBC transfusions during the index hospitalization (volume [mL] and units). Twenty-four-hour CTD (mL) will be assessed via two-sample t-test for mean difference. In the event the assumptions for a two-sample t-test are not met, a nonparametric test such as a Mann-Whitney test will be employed, with median and range values provided in the output. An additional analysis of 24-hour CTD will compare the frequency of subjects falling into volume categories (i.e., <500 mL, 500 to <750 mL, 750 to <1000 mL, 1000 to <1250 mL, 1250 to <1500 mL, and ≥ 1500 mL), and will use a Fisher-Freeman-Halton exact test to compare treatment groups. The transfusion endpoints will all be analyzed using two-sample t-tests for mean differences, and Fisher-Freeman-Halton exact tests for units. In the event the assumptions for a two-sample t-test are not met, a nonparametric test such as a Mann-Whitney test will be employed, with

median and range values provided in the output. The remaining Win Ratio component parts will also be included as secondary endpoints: proportions of fatal perioperative bleeding events will be assessed via Fisher's exact test; and proportions of UDPB events (by category) will be assessed via a Fisher-Freeman-Halton exact test. All surgical re-exploration for excessive bleeding, including those events occurring beyond the timeframe captured within the UDPB component of the primary endpoint will be captured as a secondary endpoint. Time to re-exploration will be considered.

Type I error (alpha, α) will be preserved from inflation due to multiplicity across the primary effectiveness, key secondary, and secondary endpoints via a hierarchical closed testing step-down approach. Only if preceding endpoints are declared statistically significant at the alpha 0.05 level, can further endpoints also be declared significant. The order of hierarchical testing will follow the order of primary, key secondary, and secondary endpoints as listed in the paragraph above, namely: the primary endpoint will be tested first, followed by the first key secondary endpoint (percent change in pre-CPB vs. post-CPB blood apixaban levels), followed by the second key secondary endpoint (percent change in pre-CPB vs. post-CPB blood rivaroxaban levels), followed by the first secondary endpoint (24-hour CTD), second secondary endpoint (platelet transfusions), and lastly the third secondary endpoint (pRBC transfusions).

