Prior to randomization, subjects will be stratified based on a) DOAC type (either apixaban or rivaroxaban), b) site, and c) type of planned cardiothoracic surgery [either CABG alone, or all other surgeries (including but not limited to combination cardiac procedures, and aortic interventions)]. Stratification is intended to control for potential confounding effects arising from differing drug therapies, institutional practices, and from procedure-specific CPB duration (i.e., device exposure – treatment duration) and bleeding risk.

As apixaban and rivaroxaban have a similar mechanism of action, approved use indications, bleeding risk, and response to the investigational therapy, the trial will evaluate both drugs as a **combined population** for effectiveness and safety. The intent is to have a balanced contribution of apixaban and rivaroxaban patients in the trial with each drug contributing a target minimum of 40% of the total study population at the time of final analysis.

Number of subjects:

Approximately 120 subjects will be randomized into the study (60 into each arm). Assuming a 5% dropout rate, at total of 114 subjects (57 per arm) are expected to be evaluable for effectiveness and safety.

Number of sites:

Approximately 30 investigational sites in the US will participate in the study.

Subjects must meet all inclusion criteria to be eligible to participate in the study. Subjects meeting any of the exclusion criteria are not eligible to participate in the study.

Inclusion criteria:

1. Males and females aged \geq 18
2. Written full informed consent
3. Cardiothoracic surgery requiring CPB \leq 36 hours from the last dose of either apixaban or rivaroxaban:
 - CABG alone
 - Valve repair or replacement
 - Combination surgery (i.e., CABG + valve operation)

- Aortic surgery

Only patients taking apixaban or rivaroxaban for one of the following indications are eligible for enrollment:
a) reduction of stroke/systemic embolism in nonvalvular atrial fibrillation, or b) initial or extended treatment of a venous thromboembolic event (VTE) which includes deep vein thrombosis (DVT) and/or pulmonary embolism (PE).

Exclusion criteria:

1. Cardiothoracic surgery >48 hours after last known dose of apixaban or rivaroxaban
2. Patients on low dose apixaban or rivaroxaban for prophylactic indications (see **Section 4.4.2** for details)
3. Heart-lung transplant procedures
4. Procedures for ventricular assist device (i.e., implant or revision of LVAD or RVAD)

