The primary effectiveness endpoint will be evaluated using the Win Ratio method of analysis for a hierarchical composite endpoint based on the Finkelstein-Schoenfeld test (Finkelstein and Schoenfeld, 1999; Pocock, et al., 2012) with three components: a) fatal bleeding events occurring within 48hrs of the index procedure, b) moderate, severe, or massive bleeding based on the Universal Definition of Perioperative Bleeding in Cardiac Surgery (UDPB) ≥ 2 classification, and c) 24-hour chest tube drainage (volume, mL). The Win Ratio assigns “wins”, “losses”, or “ties” between randomized groups in a serial fashion across all components of the composite endpoint adhering to the declared hierarchical order from higher to lower clinical importance.[14] [15] A ratio of “wins” greater than 1.0 favors the treatment arm; when the lower bound of a 95% confidence interval (CI) around the ratio exceeds 1.0, the treatment is shown to be statistically superior to control at alpha = 0.05. The primary effectiveness analysis will be performed in the overall study population comprised of both apixaban and rivaroxaban patients to evaluate the difference between the SOC (control) arm and the DrugSorb-ATR (investigational) arm.

The key secondary effectiveness endpoints are the pre-CPB vs. post-CPB change in drug levels (apixaban and/or rivaroxaban) measured by liquid chromatography/tandem mass spectrometry (LC/MS-MS) [drug removal endpoint]. Change in each subject's blood concentration of apixaban or rivaroxaban from immediately *before* to immediately *after* CPB will be collected and analyzed by a central core laboratory. Drug removal will be analyzed for apixaban and rivaroxaban independently.

Change from baseline in blood concentration of apixaban or rivaroxaban is defined as:

$$\frac{\text{pre-CPB [apixaban]}_{\text{blood}} - \text{post-CPB [apixaban]}_{\text{blood}}}{\text{pre-CPB [apixaban]}_{\text{blood}}} * 100\%$$

or

$$\frac{\text{pre-CPB [rivaroxaban]}_{\text{blood}} - \text{post-CPB [rivaroxaban]}_{\text{blood}}}{\text{pre-CPB [rivaroxaban]}_{\text{blood}}} * 100\%$$

Based on existing benchtop evidence, a conservative estimate of 40% reduction in blood concentration of DOAC between pre- and post- DrugSorb-ATR removal is expected, with a standard deviation of 40%, in the treatment arm. Minimal change is expected in the control arm. A two-sample t-test will be used to evaluate the difference between treatment arms.

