Pre-randomization stratification based on a) type of DOAC (either apixaban or rivaroxaban), b) study site, and c) planned operation will address potential confounding effects that may not be fully controlled in the randomization process. Stratification by DOAC type is intended to control for any

unanticipated differences between apixaban and rivaroxaban. Stratification by site is intended to control for institutional differences in standard practices, such as transfusion and re-operation protocols. Stratification by the type of planned operation will separate subjects undergoing CABG-alone from those undergoing all other cardiothoracic surgeries. The category of “all other” cardiac surgeries include combination cases (e.g., CABG + valve, double valve, etc.) and ascending aortic interventions. Compared to CABG-alone, these operations have a significantly different profile regarding bleeding risk and procedure/CPB duration. This distinction is important since device exposure is directly related to the amount of time spent on CPB. Details of the statistical considerations around the endpoints discussed above will be provided in [Section 11](#).

In summary, the objective of this randomized, double-blind investigation is to examine the ability of DrugSorb-ATR (a non-pyrogenic, sterile, single-use device designed to remove the small hydrophobic drugs, apixaban and rivaroxaban) to reduce surgical and post-surgical bleeding compared to current standard of care. Measurements of drug removal will be performed to correlate the clinical outcomes (i.e., reductions in bleeding) to reductions in circulating apixaban and rivaroxaban levels. The safety of the device in this setting will be assessed by systematic capture of all AEs at CGP level.

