6.1. Pre-randomization Stratification

Pre-randomization stratification will be performed on three levels, based on the rationale described below:

1. By preoperative DOAC type (either apixaban or rivaroxaban), to control for unanticipated differences between component drugs
2. By study site, to control for differences in institutional protocols for bleeding and transfusion management. Institutions may also differ in metrics utilized for clinical decision-making (e.g., decision to delay sternal closure, or surgical reoperation).
3. By the intended surgical procedure, to control for differing procedure-specific bleeding risks, and duration of CPB (i.e., device exposure) as detailed below:
 - CABG alone (irrespective of number of grafts); or
 - All other cardiothoracic procedures including but not limited to combination procedures (i.e., CABG + aortic/mitral valve procedures, double heart valve procedures, etc.), aortic interventions, and combination aortic + cardiac interventions. These surgeries generally require longer CPB time than CABG alone.

Of note, during the pre-procedure and intraoperative periods, the intended procedure may change due to factors that could not be adequately anticipated in advance of the procedures. These day-of-surgery changes to the planned operations may result in the completion of a procedure that a) does not align with eligibility criteria, or b) alters stratification. Any change to the intended procedure occurring on the day of surgery that is not updated in the final IxRS assignment will be considered a protocol deviation. These protocol deviations will be noted in a deviation log for data analysis considerations at the conclusion of the trial. All subjects who have any of the above changes to their intended procedures should progress through the study as per the protocol.

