6.2. Subject Randomization

All subjects will be prospectively randomized via an Interactive Voice/Web response (IxRS) system. Randomization must occur prior to the start of the cardiothoracic surgery procedure requiring CPB, but only after subject eligibility criteria is confirmed and written informed consent is provided by the subject or the subject's legally authorized representative/designated proxy. Subjects will be randomly assigned in a one to one (1:1) ratio to either the control arm (SOC) or the investigation arm (SOC + DrugSorb-ATR).

To ensure even distribution of subjects among the factors most likely to impact the primary and secondary outcomes, they will undergo pre-randomization stratification based on DOAC type, study site, and type of CT surgery. Neither the investigator nor the subjects will be told their assignment prior to surgery. See below ([Section 6.3.1](#)) for details of the randomization assignment. A copy of the randomization assignment will be maintained in a confidential file maintained by the Randomization and Unblinding Administrator. If the subject withdraws consent following randomization but prior to surgery, the reason for failure to treat according to randomization will be recorded in the subject's

study records.

To maintain the balance between sites in terms of numbers of subjects randomized, study sites will be capped at randomizing a maximum of 15% of the overall study sample (i.e., 18 subjects). Sites may be allowed to randomize beyond the cap on a case-by-case basis in consultation with the sponsor, considering overall study goals, randomization balances between sites, and prior quality of data collected by the site. For sites with a total enrollment consisting of only one type of the two eligible DOAC drugs, the randomization cap will be replaced by a maximum of 10% of the overall study sample (i.e., 12 subjects). In order to maintain the study-wise ratio of apixaban vs. rivaroxaban subjects within planned limits (a range of anywhere between 40% - 60% for each), the IxRS system will be used to limit enrollment accordingly.

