9. STUDY ASSESSMENTS AND PROCEDURES

An outline of study assessments, procedures, labs, and associated time windows is given in the **Schedule of Assessments** ([Table 6](#) in [Appendix 4](#)). Subjects will be evaluated through the Follow-up evaluation at 30 days post-operation. Assessments and procedures that are recorded as Standard of Care (SOC) within the **Schedule of Assessments** are outside of the CIP and are optional. They may be recorded if they are performed in accordance with SOC at the particular institution. Failure to record an assessment/procedure that is listed as SOC will not be a violation of protocol. Required assessments and procedures (not denoted as SOC) that are not completed or that are completed outside of the specified windows will be recorded as a protocol deviation ([Section 13.2, 13.3](#)).

Reference [Section 4.3](#) for the full list of study endpoints. These endpoints require assessment of clinical events and/or treatments, blood product transfusions, drainage volume, and laboratory parameters. Definitions of analysis populations and description of statistical analyses of endpoints are briefly described in [Section 11](#) and will be detailed in the Statistical Analysis Plan (SAP) for the study.

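### Planned surgery type is a randomisation stratum because bleeding risk differs, yet the primary win-ratio test is written without strata; stratify it by planned surgery type

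*Combined protocol and SAP*

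**What the plan says.** The reason for stratifying is prognostic and is given in several places.

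- Synopsis, investigational design: "Stratification is intended to control for potential confounding effects arising from differing drug therapies, institutional practices, and from procedure-specific CPB duration".
- Section 3, on operations other than CABG alone: "Compared to CABG-alone, these operations have a significantly different profile regarding bleeding risk and procedure/CPB duration".
- Section 6.1, third stratification factor: "By the intended surgical procedure, to control for differing procedure-specific bleeding risks, and duration of CPB".
- Section 6.2, purpose of the strata: "To ensure even distribution of subjects among the factors most likely to impact the primary and secondary outcomes".

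The primary analysis does not use the factor. Section 11.3 forms comparisons "in sequential comparisons between treatment and control arm subjects according to the hierarchical order of the components of the primary composite endpoint". The Synopsis describes wins, losses and ties assigned "between randomized groups in a serial fashion across all components of the composite endpoint adhering to the declared hierarchical order". Neither names a stratum, weight or covariate for the test, the win ratio or its confidence interval. Nor do the power work in Section 11.1 (including Table 3) or the interim boundaries in Section 11.6. Planned surgery type reappears only as a subgroup factor, in the Synopsis and in Section 11.4.

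Section 9 says that the endpoint analyses are only briefly described in Section 11 "and will be detailed in the Statistical Analysis Plan (SAP) for the study". That further detail is not in the documents available.

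**The concern.** The plan names a factor as prognostic for bleeding, randomises within it, and then tests a bleeding endpoint as if it did not exist. Some pairwise wins and losses will then reflect the operation rather than the device. This adds noise. If assignment is balanced within surgery type, the unstratified variance is also too large, so the test rejects less often than its nominal 5%.

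This matters only if two things are true: the real effect is smaller than planned, and surgery type is clearly prognostic. The first is plausible, because Section 11.1 calls the outcome literature for this population limited and takes its effect from the assumptions of another trial. The second is asserted in Section 3, but no size is given.

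**Working it through.** **Inputs from the documents.** 114 evaluable subjects, 1:1 (Section 11.1). Fatal bleeding 3% in both arms; UDPB class 2 or higher 40.5% control and 24.3% treatment; 24-hour drainage 800 and 480 mL, SD 253 (Table 3, equal-drug rows). Interim at 70% with Z 2.44, final Z 2.00 (Section 11.6). The O'Brien-Fleming-type spend at information 0.7 is 0.0148 (Z 2.44), and the pair 2.44/2.00 gives an overall two-sided alpha of 0.0500.

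**Assumptions not in the documents.** 40% CABG alone; the gap between surgery types; smaller effects of 25% (UDPB 40.5 × 0.75 = 30.4%, drainage 800 × 0.75 = 600 mL) and 30%. Gaps are placed around the overall mean and total SD is held at 253. The share of drainage variance explained by surgery type is then 0.4 × 0.6 × gap² / 253²: 3.7% at 100 mL, 15.0% at 200 mL, 33.7% at 300 mL.

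**Test.** Each subject's score U is wins minus losses against all others in the comparison set. T is the sum of U over treated subjects, with permutation variance V = n₁n₀ / [n(n−1)] × ΣU². Unstratified: Z = T/√V. Stratified: Z = Σ wₛTₛ / √(Σ wₛ²Vₛ), with scores formed within stratum s and wₛ = 1/nₛ.

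**Step 1: reproduce Table 3 (equal drugs, 50:50; 39 and 56 per arm).** The unstratified simulation gives 91.2% at the interim (stated 91.3%) and 99.7% at the end (stated 99.5%). The stated figures are therefore consistent with an unstratified test.

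**Step 2: final look, 114 subjects, 25% effect.** Ranges span three allocation schemes: blocks of 4 within surgery × DOAC; blocks of 4 within site × surgery × DOAC; simple randomisation.

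| Gap (drainage / UDPB) | Unstratified | Stratified | Change, points |
|---|---|---|---|
| none | 81.1–82.1% | 80.6–81.7% | −0.5 to −0.4 |
| 100 mL / 10 points | 81.0–82.7% | 81.8–83.4% | +0.6 to +0.8 |
| 200 mL / 20 points | 80.9–81.5% | 85.1–85.6% | +3.6 to +4.4 |
| 300 mL / 30 points | 80.1–83.0% | 91.3–91.7% | +8.7 to +11.2 |

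Each setting has 10,000 trials, so the Monte Carlo SE is √(0.8 × 0.2 / 10,000) = 0.4 point; differences are paired. Separately coded simulations gave the same pattern, with a cost of up to about 1 point with no gap and gains of up to about 7 points at 200 mL and 13 at 300 mL. At a 30% effect the change is −0.4 to −0.1 with no gap, +1.4 to +2.1 at 200 mL and +3.0 to +5.1 at 300 mL. At the planned 40% effect, power is 99.5–99.7% unstratified and 99.4–100% stratified.

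**Step 3: interim crossing at the planned effect, first 80 subjects.** With no gap, 91.4–93.0% becomes 90.3–92.5%, a cost of 0.5 to 1.1 points. The change is −0.1 to +0.2 at 100 mL, +1.6 to +2.6 at 200 mL and +3.9 to +5.2 at 300 mL. Judged by the win-ratio confidence interval instead, the no-gap interim cost is 1.0 to 1.3 points.

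**Step 4: two-sided type I error over both looks.**

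| Allocation | Test | No gap | 200 mL | 300 mL |
|---|---|---|---|---|
| Blocks, surgery × DOAC | unstratified | 4.8% | 3.7% | 2.1% |
| | stratified | 4.8% | 4.9% | 5.0% |
| Blocks, site × surgery × DOAC | unstratified | 4.8% | 4.2–4.5% | 3.4–3.8% |
| Simple | unstratified | 5.1% | 4.9% | 5.1% |
| | stratified | 4.9% | 5.0% | 4.9% |

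Stratified error under the site-based blocks is also about 5%.

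**Step 5: which strata and weights.** Weights matter. With 30% CABG, 200 mL / 20 points and half the planned effect, an unweighted sum over strata gave no gain (62.8% unstratified, 62.7% stratified), while 1/nₛ weights raised power from 62.1% to 68.3%. Adding DOAC type (four strata, drug not prognostic, as the plan assumes) gave 0.5 to 1.3 points less than surgery type alone at a 25% effect. Site cannot be an analysis stratum: 120 / 30 = 4 subjects per site, and 2 × 30 × 2 = 120 cells for 120 subjects.

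**The case against.** The strongest reply is that nothing is broken. The unstratified test is valid, the power target is met with room to spare, and the protocol offers stratified randomisation itself as the control for confounding; it nowhere promises a stratified test. All of that stands, and it limits the point to an efficiency suggestion.

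Second, silence in Section 11.3 is not proof that the detailed analysis plan is unstratified. That also stands. If that plan already stratifies, only Sections 11.1, 11.3 and 11.6 need aligning. But strata and weights decide which pairs count, and Section 11.3 is where the primary test and its success criterion are set out.

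Third, every gain rests on assumed figures. A 300 mL gap has one binary factor explaining about a third of drainage variance, and should be read as an extreme case. At 100 mL / 10 points the gain is under 1 point. If only one component differs, the gain at a 25% effect is 2.3 points (200 mL in drainage alone, 83.5% to 85.8%) or 1.0 point (20 UDPB points alone, 82.1% to 83.1%). These limits stand. Against them, the loss if surgery type is irrelevant is about 1 point.

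Fourth, only one of three randomisation factors would enter the test, and the benefit depends on the weighting. Both are true. Site is too sparse to use, and the weights can be fixed in advance.

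**Conclusion.** The point holds as an optional, low-cost improvement, not as an error. The plan calls surgery type prognostic for bleeding and does not use it in the primary bleeding test. At the planned effect, final power does not depend on the choice. If the true effect is nearer 25% and the surgery types differ by about 200 mL and 20 UDPB points, stratifying adds about 4 points of final power, and as many as 7 in some simulations. If surgery type is not prognostic, it costs about 1 point at most at the final look and about 0.5 to 1.3 points of interim crossing probability. Under balanced allocation with a 200 mL gap, the unstratified test spends about 3.7 to 4.5% of its 5%; the stratified test spends about 5%. These sizes depend on the assumed CABG share, gaps, smaller effects and block scheme. The direction follows from how prognostic surgery type is.

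**What to change.** 1. Add to Section 11.3 and the SAP, for example: *The primary Finkelstein-Schoenfeld test and win ratio are stratified by planned surgery type (CABG alone versus all other) as recorded in the final IxRS assignment. Pairs are formed within strata and each stratum is weighted by 1/stratum size. The win ratio is the weighted sum of wins over the weighted sum of losses, with its confidence interval on the log scale from the within-stratum U-statistic variances and the same weights. The same test is used at the interim and final looks. The unstratified version is a sensitivity analysis.*
2. Use the IxRS value rather than the operation performed. Section 6.1 foresees late changes and classes as a protocol deviation "Any change to the intended procedure occurring on the day of surgery that is not updated in the final IxRS assignment".
3. Leave site out of the primary test. DOAC type may be added, but it showed no further gain.
4. Rerun Table 3 and the Section 11.6 stopping probability for the stratified test. With no gap, the equal-drug interim row moves from 91.2% to 90.5%, and the row stated as 88.1% simulates at 89.2% unstratified and 88.7% stratified.
5. Record the small loss expected if surgery type is not prognostic.

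The cost is wording, code for the stratified test and interval, the rerun, and a protocol amendment handled under Section 16. It should be done before any unblinded look. Sample size and trial conduct do not change.
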